Based on the foregoing, there is a strong rationale to allow use of the 0.5-mL dose for young children. Consequently, the purpose of the study described herein is to describe the safety and immunogenicity of the 0.5-mL dose (15 μ g HA per strain) of Fluzone Quadrivalent vaccine in children 6 through 35 months of age, with the intent to modify the vaccine's Prescribing Information (Dosage and Administration) to show the 0.5-mL dose of Fluzone Quadrivalent vaccine as indicated for all ages 6 months and older, including children 6 months through 8 years of age (who might receive 1 or 2 doses as recommended by the ACIP).

2 Trial Objectives

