12.1.2.2 Statistical Methods

- Geometric mean titers: The statistical methodology will be based on a 2-sided 95% CI of the ratio of the GMTs (0.5-mL dose divided by 0.25-mL dose) at 28 (window, 28–35) days after the final vaccination. Non-inferiority for GMTs will be demonstrated if the lower limit of the 2-sided 95% CI of the GMT ratio is > 0.667 for each of the 4 virus strains. The 95% CI will be calculated using normal approximation of log-transformed titers. The Per-Protocol Analysis Set (PPAS) will be used as the primary analysis set for this objective.
- Seroconversion: The statistical methodology will be based on a 2-sided 95% CI of the difference in seroconversion rates (0.5-mL dose minus 0.25-mL dose) at 28 (window, 28–35) days after the final vaccination. Non-inferiority for seroconversion will be demonstrated if the lower limit of the 2-sided 95% CI is $> -10\%$ for the 4 strains. The 95% CI of the rate difference will be computed using the Wilson Score method without continuity correction. The PPAS will be used as the primary analysis set for this objective.

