### 5.1.1.2 Statistical Methods

The 0.5-mL dose of Fluzone Quadrivalent vaccine will be demonstrated as non-inferior to the 0.25-mL dose of Fluzone Quadrivalent vaccine in terms of fever reaction through an assessment of the rates of any fever (temperature  $\geq 100.4^{\circ}\text{F}$  [ $38.0^{\circ}\text{C}$ ]) during the day of vaccination or during the 7 days following any dose (Dose 1 and Dose 2 combined).

Non-inferiority will be demonstrated if the upper bound of the 2-sided 95% CI of the rate difference between Group 2 (subjects receiving 0.5 mL of vaccine) and Group 1 (subjects receiving 0.25 mL of vaccine) is  $< 5\%$ . The 95% CI of the difference in proportions  $P_{0.5\text{mL}} - P_{0.25\text{mL}}$  will be computed using the Wilson Score method without continuity correction as quoted by Newcombe (3).

To test this hypothesis, a 2-sided 95% CI will be constructed around the difference,  $P_{0.5\text{mL}} - P_{0.25\text{mL}}$ , where  $P_{0.25\text{mL}}$  and  $P_{0.5\text{mL}}$  are the proportions of subjects in Group 1 and Group 2, respectively, experiencing any fever (temperature  $\geq 100.4^{\circ}\text{F}$  [ $38.0^{\circ}\text{C}$ ]) during the day of vaccination or during the 7 days following any dose (Dose 1 and Dose 2 combined).

The hypothesis will be supported by the data, if the upper bound of the calculated 95% CI is  $< 5\%$ . This is the equivalent to testing the null hypothesis using a 1-sided type I error rate of 0.025.

$$H_0: P_{0.5\text{mL}} - P_{0.25\text{mL}} \geq 5\%$$

$$H_A: P_{0.5\text{mL}} - P_{0.25\text{mL}} < 5\%$$

If the null hypothesis is rejected, then the alternative hypothesis of non-inferiority will be supported.

Because of concerns regarding the integrity of safety data collected at Site 009, an additional statistical analysis will be conducted that excludes temperature data collected at this site. The results of this analysis will be reported in the CSR appendices.

Nevertheless, the study conclusion (non-inferiority with respect to the proportion of subjects with fever in Group 1 vs Group 2) will be based on the primary analysis that includes data from Site 009.

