## 5.1.2.2 Statistical Methods

### 5.1.2.2.1 Geometric Mean Titers

The statistical methodology will be based on a 2-sided 95% CI of the ratio of the GMTs (0.5-mL dose divided by 0.25-mL dose) at 28 (window, 28–35) days after the final vaccination.

Non-inferiority for GMTs will be demonstrated if the lower limit of the 2-sided 95% CI of the GMT ratio is > 0.667 for each of the 4 virus strains (A/H1N1, A/H3N2, B1 and B2). The 95% CI will be calculated using normal approximation of log-transformed titers.

For the separately virus strain (A/H1N1, A/H3N2, B1 and B2), the primary parameter will be the difference of the means of the log10-transformed post-vaccination titers between GMT0.5mL and GMT0.25mL.

Each hypothesis will be supported by the data if the upper bound of the calculated 95% CI is > 0.667. This is the equivalent to testing the null hypothesis using a 1-sided type I error rate of 0.025.

For each virus strain (A/H1N1, A/H3N2, B1 and B2), the null hypothesis and the alternative hypothesis, are:

$$H_0: \text{GMT}_{0.5\text{mL}} / \text{GMT}_{0.25\text{mL}} \leq 0.667$$

$$H_A: \text{GMT}_{0.5\text{mL}} / \text{GMT}_{0.25\text{mL}} > 0.667$$

or equivalently,

$$H_0: \log_{10}(\text{GMT}_{0.5\text{mL}}) - \log_{10}(\text{GMT}_{0.25\text{mL}}) \leq \log_{10}(0.667)$$

$$H_A: \log_{10}(\text{GMT}_{0.5\text{mL}}) - \log_{10}(\text{GMT}_{0.25\text{mL}}) > \log_{10}(0.667)$$

For the separately considered GMT hypotheses, if the null hypothesis is rejected, then the alternative hypothesis of non-inferiority will be supported.

The 2-sided 95% CI for the ratio of GMTs (GMT0.5mL / GMT0.25mL) will be calculated using normal approximation of log-transformed concentrations.

The 95% CI for the GMT ratio between 2 groups will be constructed as follows: Logarithm transformation of the individual concentrations will be calculated. Assuming that individual log10 (concentration) is normally distributed, the 95% CI for the difference in log10 (GMT) between 0.5-mL (or Groupi) and 0.25-mL (or Groupj) will be in the form:

$$\bar{X}_i - \bar{X}_j \pm t(1-\alpha/2, n_i + n_j - 2) \times S \sqrt{1/n_i + 1/n_j}$$

where  $\bar{X}_i = \log_{10}$  (GMC) is the mean of log10 (concentration) of Group *i*,

$S^2 = [(n_i - 1) S_i^2 + (n_j - 1) S_j^2] / (n_i + n_j - 2)$  is the pooled sample variance,

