#### 5.1.2.2.2 Seroconversion

The statistical methodology will be based on a 2-sided 95% CI of the difference in seroconversion rates (0.5-mL dose minus 0.25-mL dose) at 28 (window, 28–35) days after the final vaccination. Non-inferiority for seroconversion will be demonstrated if the lower limit of the 2-sided 95% CI is  $> -10\%$  for the 4 strains (A/H1N1, A/H3N2, B1 and B2). The 95% CI of the rate difference will be computed using the Wilson Score method without continuity correction.

For each virus strain (A/H1N1, A/H3N2, B1 and B2), the null hypothesis and the alternative hypothesis, are:

$$H_0: P_{0.5mL} - P_{0.25mL} \leq -10\%$$

$$H_A: P_{0.5mL} - P_{0.25mL} > -10\%$$

For the separately considered seroconversion hypotheses, if the null hypothesis is rejected, then the alternative hypothesis of non-inferiority will be supported.

The CI of the difference in proportions  $P_{0.5mL} - P_{0.25mL}$  will be computed using the Wilson Score method without continuity correction, quoted by Newcombe (3).

For descriptive purposes, the statistics presented in Table 5.1 will be produced.

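### The SAP gives two success rules for each secondary endpoint, all four strains and strain by strain, and no readable section ties the secondary tests to the fever result or to each other

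*SAP*

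**What the plan says.** **Fever.** SAP 5.1.1.2 sets one test: "The hypothesis will be supported by the data, if the upper bound of the calculated 95% CI is" below 5%. It adds: "This is the equivalent to testing the null hypothesis using a 1-sided type I error rate of 0.025". The rule does not mention the secondary tests.

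**GMT.** Protocol 12.1.2.2 has one rule, that "the lower limit of the 2-sided 95% CI of the GMT ratio is > 0.667 for each of the 4 virus strains". SAP 5.1.2.2.1 begins with the same rule: non-inferiority is "demonstrated if the lower limit of the 2-sided 95% CI of the GMT ratio is > 0.667 for each of the 4 virus strains". The section then adds two per-hypothesis statements. One is "Each hypothesis will be supported by the data if the upper bound of the calculated 95% CI is > 0.667", followed by a stated one-sided error rate of 0.025. The other is "For the separately considered GMT hypotheses, if the null hypothesis is rejected, then the alternative hypothesis of non-inferiority will be supported".

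**Seroconversion.** Protocol 12.1.2.2 and the opening of SAP 5.1.2.2.2 require the lower limit to exceed -10% for the four strains. The SAP section then adds: "For the separately considered seroconversion hypotheses, if the null hypothesis is rejected, then the alternative hypothesis of non-inferiority will be supported".

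**Links between tests.** The lead-in at SAP 5.1.2 names the analysis set and nothing else. The SAP table of contents lists no multiplicity section. SAP 5.7 records no changes to the planned analyses. Protocol 12.5 and SAP 5.5 (sample size and power) are redacted.

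**The concern.** Suppose three of four strains clear the GMT margin. The opening rule says GMT non-inferiority is not demonstrated. The later sentence can be read to say it is supported for three strains. The study report could follow either rule and cite the SAP for it.

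The second gap is order. On the readable text, an immunogenicity conclusion could be drawn after fever non-inferiority has failed, or on GMT without seroconversion, or the reverse. This matters because the secondary objective is a formal test with margins and a stated error rate, and Protocol 1.4 says the sponsor means to revise the Prescribing Information "to show the 0.5-mL dose of Fluzone Quadrivalent vaccine as indicated for all ages 6 months and older". What counts as success should be fixed before the data are seen.

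**Working it through.** **Inputs.** Two-sided 95% intervals throughout (Protocol 12.1.1.2 and 12.1.2.2; SAP 5.1.1.2, 5.1.2.2.1, 5.1.2.2.2). One fever test, four GMT tests, four seroconversion tests. No interim analysis (Protocol 12.4). The documents give no correlations between tests, so those below are assumptions shown as a range.

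**1. The plan's own figure.** (1 - 0.95)/2 = 0.025. This reproduces the stated one-sided rate, using the upper limit for fever and the lower limit for GMT. For seroconversion the rate is implied by the interval and not stated.

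**2. One endpoint under the all-four rule.** If at least one strain is truly at or beyond its margin, a false success requires that strain to pass, so P(all four pass) ≤ 0.025. No adjustment is needed within an endpoint.

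**3. Three objective-level claims under the all-four rule, with no order.**
- Upper bound: 3 × 0.025 = 7.5%. If independent and each at full size: 1 - 0.975^3 = 7.3%.
- Full size requires fever at its margin and, for each endpoint, one strain at its margin with the other three far above.
- With every null at its margin and independent tests, an all-four pass has probability 0.025^4 = 3.9 × 10^-7. The three-claim error is then 1 - 0.975 × (1 - 3.9 × 10^-7)^2, about 2.5%.
- With every null at its margin and positive correlation among the eight secondary tests (same strain 0.5 to 0.9, different strains 0.2 to 0.7, fever independent; 1,000,000 simulated draws), it is 2.5% to 2.9%.

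**4. If each strain-level rejection is a claim in its own right.** Every null at its margin:

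| Claims | Independent | Upper bound | Assumed correlation, same range as in step 3 |
|---|---|---|---|
| 8 secondary | 1 - 0.975^8 = 18.3% | 8 × 0.025 = 20% | 15.5% down to 8.6% |
| 9 with fever | 1 - 0.975^9 = 20.4% | 9 × 0.025 = 22.5% | 17.6% down to 10.9% |

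**5. The upper-bound sentence.** At a true GMT ratio of 0.667, the upper limit exceeds 0.667 with probability 1 - 0.025 = 97.5%. Taken literally, the sentence contradicts both the lower-limit rule and the 0.025 in the same section.

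**6. After the change.** Test fever first at 0.025.
- If GMT and seroconversion must both pass, the secondary objective is one all-eight test of size at most 0.025.
- If they are tested in a fixed order, any false claim requires the first true null in the sequence to be falsely rejected, again with probability at most 0.025.

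Either way the overall error is at most 2.5% with unchanged intervals.

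**The case against.** The strongest reply is that there is only one rule. The protocol has the all-four criterion alone, and each SAP section opens with it. The later sentence closes the display of null and alternative hypotheses for each strain, and a near-identical sentence closes the fever display. It can be read as saying what rejecting a component null means, without creating a second route to success. No section announces a strain-specific claim. There is also a single secondary objective (Protocol 2.2, SAP 2.2) that joins GMT ratios and seroconversion differences with *and*, which leans towards requiring both.

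Much of this stands. A reader might infer from the SAP that nine claims are planned with a roughly 20% chance of a false one. The documents do not support that: it requires the strain-level sentences to override the rule that opens each section and is the only one in the protocol. It also requires every null to sit at its margin. That would mean a GMT ratio of 0.667 and a 10-point loss of seroconversion for all four strains at double the antigen. The dose-comparison trials summarised in Protocol 1.4 report full-dose responses that were higher than, or not different from, half-dose responses.

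What does not fall away is the ambiguity. The SAP never says that the strain-level rejections are components only, and it uses the same verb, supported, for the conclusion of the single fever test. SAP 5.1.2 speaks of secondary objectives in the plural. Nothing readable places the secondary tests after fever. A statement in the redacted sections cannot be excluded, but the sections that set the decision rules are readable and contain none.

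**Conclusion.** The point holds as a wording defect with a modest statistical consequence. SAP 5.1.2.2.1 and 5.1.2.2.2 each contain two rules that can give different answers when some strains pass and others fail. The readable text also leaves the relation among fever, GMT and seroconversion open.

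On the all-four reading, which the protocol supports, each endpoint is held at 2.5%. The three objective-level claims are bounded by 7.5%, a figure approached only in the configuration described in step 3. The 18.3% and 20.4% figures apply only on the strain-level reading with independent tests, and fall under the assumed positive correlations.

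Two further inferences should be resisted. The primary fever result is not inflated: it is a single test at one-sided 2.5%. And the upper-bound sentence is best taken as a drafting slip, since the same section states the lower-limit rule and the 0.025 rate. Confidence is medium because the sample-size sections cannot be read.

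**What to change.** Three edits to the SAP:

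1. Delete the per-hypothesis sentences that close SAP 5.1.2.2.1 and 5.1.2.2.2, or reword them so that each strain-level rejection is a component of the all-four rule in Protocol 12.1.2.2.
2. In SAP 5.1.2.2.1, change the sentence that compares the upper bound with 0.667 so that it refers to the lower bound. Deleting the sentences in edit 1 alone would leave this strain-level rule in place.
3. State that the secondary tests are confirmatory only if fever non-inferiority is shown. Then either require both GMT and seroconversion, or test them in a stated order. Requiring all eight tests jointly is one option and not a necessity. Where a condition is not met, report the strain-level intervals as descriptive.

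Margins, intervals and sample size stay as they are. The cost is in what may be claimed: no confirmatory immunogenicity conclusion if the fever test fails, and no confirmatory strain-specific conclusion if one strain fails. The effect of requiring both endpoints on power cannot be checked because the power section is redacted. If the sponsor does want strain-level claims, the SAP should say so and allocate alpha, for example 0.025/8 = 0.003125 one-sided per test after a successful fever test.

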#### 5.1.2.2.2 Seroconversion

The statistical methodology will be based on a 2-sided 95% CI of the difference in seroconversion rates (0.5-mL dose minus 0.25-mL dose) at 28 (window, 28–35) days after the final vaccination. Non-inferiority for seroconversion will be demonstrated if the lower limit of the 2-sided 95% CI is  $> -10\%$  for the 4 strains (A/H1N1, A/H3N2, B1 and B2). The 95% CI of the rate difference will be computed using the Wilson Score method without continuity correction.

For each virus strain (A/H1N1, A/H3N2, B1 and B2), the null hypothesis and the alternative hypothesis, are:

$$H_0: P_{0.5mL} - P_{0.25mL} \leq -10\%$$

$$H_A: P_{0.5mL} - P_{0.25mL} > -10\%$$

For the separately considered seroconversion hypotheses, if the null hypothesis is rejected, then the alternative hypothesis of non-inferiority will be supported.

The CI of the difference in proportions  $P_{0.5mL} - P_{0.25mL}$  will be computed using the Wilson Score method without continuity correction, quoted by Newcombe (3).

For descriptive purposes, the statistics presented in Table 5.1 will be produced.

### 5.1.3 Statistical Methods for Observational Objectives

For the main safety and immunogenicity parameters, 95% CIs of point estimates will be calculated using the normal approximation for quantitative data and the exact binomial distribution (Clopper-Pearson method) for proportions.

### 5.1.3.1 Safety Analysis

The safety analysis will report the occurrence of solicited reactions and the incidence of unsolicited AEs between Visit 1 and Visit 2 (or between Visit 1 and Visit 3 for those subjects receiving 2 doses).

To avoid any under-estimation of the incidences, the number of subjects with documented safety will be used as denominator for the frequencies.

- For solicited reactions, the denominator will be the total number of subjects who have non-missing data for the endpoint considered
- For unsolicited AEs, the denominator will be the total number of subjects who were vaccinated at the dose analyzed.

The safety tables will be produced using a subject approach, i.e., number of subjects who experienced at least 1 safety event during a considered period.

The 2-sided 95% CIs for the percentages will be calculated using the exact binomial method (Clopper-Pearson method).

Additional safety tables, which will be based on analyses that exclude safety data from Site 009, will be presented in the CSR appendices. Specifically, these tables will be those that provide overall safety overviews/summaries and those that describe solicited reactions after any vaccination by maximum intensity.

#### *Solicited reactions*

The solicited injection site reactions and the solicited systemic reactions will be presented separately (except in summary tables).

Solicited reactions will be presented according to their nature (MedDRA [19.0] PT), intensity (Grade 1, 2, or 3), time of onset, and number of days of occurrence.

#### *Unsolicited AEs*

Unsolicited AEs included in the analysis will be summarized in the safety overview and analyzed according to their nature (MedDRA [19.0] system organ class and PT classification) and relationship to the vaccination.

#### *Injection Site Reactions*

For each treatment group, the number and percentage of subjects experiencing any injection site reaction after injection will be calculated.

The description of injection site reactions will be presented according to:

- Solicited injection site reactions
  - All solicited injection site reactions that occur each day within 7 days after injection will be analyzed.
- Unsolicited injection site reactions

- All unsolicited injection site reactions between Visit 1 and Visit 2 (or between Visit 1 and Visit 3 for those subjects receiving 2 doses) will be described according to the type of events.

### ***Systemic Events and Reactions***

For each treatment group, the number and percentage of subjects experiencing any unsolicited immediate systemic event in the 20 minutes after injection will be calculated.

In addition, the description of systemic events will be structured according to:

- Solicited systemic reactions

All solicited systemic reactions that occur each day within 7 days after injection will be analyzed.

- Unsolicited systemic events

All unsolicited systemic events between Visit 1 and Visit 2 (or between Visit 1 and Visit 3 for those subjects receiving 2 doses) will be described according to the type of events.

### ***Serious Adverse Events***

The number and percentage of subjects with SAEs after vaccination within 28 days after each vaccination in each treatment group will be calculated by outcome, seriousness, and relationship to vaccination.

